1.2. Estimands

1.2.1. Primary Estimand

The primary clinical question of interest is: What is the impact of MTD of tirzepatide (10 mg or 15 mg) QW, compared with placebo, on the maintenance of weight loss after an initial 36-week open-label tirzepatide lead-in treatment period, in study participants who do not have T2DM, and have obesity ($\text{BMI} \geq 30 \text{ kg/m}^2$) or are overweight ($\text{BMI} \geq 27 \text{ kg/m}^2$) with at least 1 weight-related comorbid condition?

For primary disclosure of Study GPHN including submission to the US FDA

The estimand is described by the following attributes:

- Population: patients qualifying for study entry per protocol inclusion/exclusion criteria who reach and tolerate either tirzepatide 10-mg or 15-mg dose at Visit 11(Week 36).
- Endpoint: percent change in body weight from randomization (Week 36) to 88 weeks.
- Treatment condition of interest: tirzepatide MTD versus placebo, regardless of study drug adherence.
- Handling of intercurrent events (ICEs): The ICEs leading to treatment discontinuation for any reason are addressed by the treatment condition of interest attribute and handled by

treatment policy strategy as described in the International Council for Harmonisation (ICH) E9 (R1) Addendum (ICH 2019). Further details can be found in Section 4.3.2.3.

- Population-level summary: difference in mean between treatment conditions.

Rationale for estimand: the primary estimand was requested by US FDA; it aims at reflecting how participants are treated in clinical practice, irrespective to the compliance to planned course of treatment.

This *de facto estimand* is referred as the “treatment regimen” estimand in the latter sections of this document, which is equivalent to the “hybrid” estimand in the protocol.

For all other purposes

The estimand is described by the following attributes:

- Population: patients qualifying for study entry per protocol inclusion/exclusion criteria who reach and tolerate either tirzepatide 10-mg or 15-mg dose at Visit 11(Week 36).
- Endpoint: percent change in body weight from randomization (Week 36) to 88 weeks.
- Treatment condition of interest: tirzepatide MTD versus placebo, excluding data after discontinuation of study drug.
- Handling of ICEs: The ICEs leading to treatment discontinuation for any reason are addressed by the treatment condition of interest attribute and handled by the hypothetical strategy as described in the ICH E9 (R1) Addendum (ICH 2019).

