- Population-level summary: difference in mean between treatment conditions.

Rationale for estimand: this estimand aims at reflecting treatment efficacy in an envisaged scenario in which the intercurrent events leading to treatment discontinuation would not occur.

We will refer to this estimand as “efficacy” estimand in the latter sections.

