Unless specified otherwise, for analyses in the double-blind treatment period, baseline is defined as the last nonmissing data collected prior to or at randomization (Week 36); for analyses including data collected in open-label lead-in period, baseline is defined as the last nonmissing data collected prior to or at study enrollment (Week 0).

For some specific safety related parameters, the definition of baseline and postbaseline for double-blind treatment period are specified in [Table GPHN.4.1](#).

The definition of baseline and postbaseline during the open-label lead-in treatment period can be found in [Appendix 4](#).

Table GPHN.4.1. Baseline and Postbaseline Definitions for Safety Outcomes in Double-Blind treatment Period

Analysis Set	Analysis Type	Baseline	Postbaseline
SS	1.1) Treatment-Emergent Adverse Events	Ongoing at the time of the randomization to the double-blind treatment period.	Starts after randomization visit and ends after the whole study period (including off-drug follow-up visit).
SS	1.2) Treatment-Emergent Abnormal Labs ^a , Vital Signs, and ECGs.	Refer to Table GPHN.6.1 for baseline definition.	Postbaseline will be defined as above (1.1). All scheduled and unscheduled measurements will be included.
SS	1.4) Change from Last Baseline to Week xx and to Last Postbaseline for Labs ^a , Vital Signs, and ECGs.	The last scheduled and unscheduled non-missing assessment recorded during the open-label lead-in period.	Postbaseline will be defined as above (1.1). Only scheduled visits will be included. The ED visits are considered scheduled visits.

Abbreviations: ECGs = electrocardiogram; ED = early discontinuation; SS = Safety Analysis Set.

^a Immunogenicity-related analysis is specified in Section [4.6.5.5](#).

For the primary and key secondary efficacy endpoint analyses subject to type 1 error rate control, data for participants with missing values at the 88-week visit (or weight-related measurements at 64-week visit) will be imputed based on the method described in Section [4.3.2.3](#). Otherwise, missing values will not be explicitly imputed except for the parameters with only 1 postbaseline measure during the analysis period per schedule of activity, where LOCF approach will be applied to impute the endpoint when ED measure is available.

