4.4.3. Additional Secondary Endpoint(s)

Unless otherwise specified, other secondary efficacy analyses will be guided by the efficacy estimand using the same population as for primary analysis.

Analyses for labs including fasting glucose, hemoglobin A1c, fasting insulin, and lipid parameters will be performed for both SI units and CN units.

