4.4.3.1. Additional Secondary Efficacy Analyses

Table GPHN.4.3. Secondary Efficacy Measures Not Controlled for Type 1 Error

Analysis variable	Analysis set	Analysis method	Additional Information
Mean change in measurements of lab tests and vital sign	Data from randomization (Week 36) to Week 88	MMRM model with treatment group, visit, treatment-by-visit interaction, all stratification factors as fixed effects, and the corresponding value at randomization (Week 36) as a covariate	Variance-covariance

Analysis variable	Analysis set	Analysis method	Additional Information
			structure for within-patient errors will be same as Section 4.3.2.2. LSM estimates may be plotted by treatment through 88 weeks. Log transformation will be adopted for fasting insulin and lipid parameters.
Mean change in SF-36 v2 acute form domain score in 
 • Physical Functioning domain (PF) • Role-Physical domain (RP) • Role-Emotional domain (RE) • Mental Health domain (MH) Mean change in IWQOL-Lite-CT Physical Function composite score		ANCOVA model with terms of treatment group, all stratification factors, and the corresponding value at randomization (Week 36) as a covariate.	Missing data will be imputed using LOCF.
Mean change in measurements of lab tests and vital signs	Data from Week 0 to Week 88	MMRM model with treatment group, visit, treatment-by-visit interaction, all stratification factors, and the corresponding value at baseline (Week 0) as covariates.	Variance-covariance structure for within-patient errors will be same as Section 4.3.2.2. LSM estimates may be plotted by treatment through 88 weeks. Log transformation will be adopted for fasting insulin and lipid parameters.
Mean change in body weight, BMI, and percent change in body weight		MMRM model with treatment group, visit, treatment-by-visit interaction, country/pooled country and sex as fixed effects, and the corresponding value at baseline (Week 0) and at randomization (Week 36) as covariates.	Variance-covariance structure for within-patient errors will be same as Section 4.3.2.2. LSM estimates may be plotted by treatment through 88 weeks.

Analysis variable	Analysis set	Analysis method	Additional Information

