Mean change in waist circumference		MMRM model with treatment group, visit, treatment-by-visit interaction, all stratification factors as fixed effects, and the corresponding value at baseline (Week 0) as covariates.	Variance-covariance structure for within-patient errors will be same as Section 4.3.2.2. LSM estimates may be plotted by treatment through 88 weeks.
Mean change in SF-36 v2 acute form in 
 Physical Functioning domain (PF) and 
 IWQOL-Lite-CT in 
 Physical Function composite score 		ANCOVA model with terms of treatment group, all stratification factors, and the corresponding value at baseline (Week 0) as covariates.	Missing data will be imputed using LOCF.

Abbreviations: ANCOVA = analysis of covariance; BMI = body mass index; IWQOL-Lite-CT = Impact of Weight on Quality of Life-Lite-Clinical Trials Version; LOCF = last observation carried forward; LSM = least squares mean; MMRM = mixed model for repeated measures; SF-36 v2 acute form = Short Form-36 Version 2 Health Survey acute form.

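### Patient-reported outcomes are imputed by LOCF under a hypothetical estimand that LOCF does not target, and the Week 0-to-88 row does not say which score may be carried

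*SAP*

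**What the plan says.** SAP 4.4.3 states that "other secondary efficacy analyses will be guided by the efficacy estimand using the same population as for primary analysis". SAP 4.7.1 places the PRO questionnaires on the Efficacy Analysis Set (EAS), which SAP section 3 limits to double-blind data up to 7 days after the last dose. SAP 1.2.1 assigns treatment discontinuation to the hypothetical strategy and describes the target as "treatment efficacy in an envisaged scenario in which the intercurrent events leading to treatment discontinuation would not occur".

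Table GPHN.4.3 analyses SF-36 domain scores and the IWQOL-Lite-CT Physical Function composite by ANCOVA with the instruction "Missing data will be imputed using LOCF". It does so for change from Week 36 and again for change from Week 0. The second block has the scope "Data from Week 0 to Week 88" and covers two scores, SF-36 Physical Functioning and the IWQOL-Lite-CT composite. Table GPHN.4.4 applies the same method to the exploratory PRO scores, from Week 36 only.

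The general rule in SAP 4.1 is narrower. Outside the primary and key secondary endpoints, gaps are left unfilled "except for the parameters with only 1 postbaseline measure during the analysis period per schedule of activity". For that group of parameters the rule turns to LOCF, and only if there is an ED score to carry.

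**The concern.** There are two problems.

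The first is a mismatch between method and estimand. A participant who stops treatment and has no on-treatment Week 88 score is given an earlier score as if it were the Week 88 result. The estimand asks for the Week 88 score under continued assigned treatment. In a withdrawal design the arms are expected to move apart over 52 weeks, so an early score and a Week 88 score are different quantities. Imputing one value and treating it as data also leaves out the uncertainty of the imputation.

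The second is an unresolved conflict over which score is carried in the Week 0-to-88 row. Measured from Week 0, both Week 36 and Week 88 are scheduled scores after baseline, so the one-measure condition in SAP 4.1 is not met. The table still prescribes LOCF and sets no limit on it. One programmer could carry only an ED score. Another could carry the open-label Week 36 score when no usable ED score exists. The two give different analysed samples and different estimates.

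At stake are the estimates and intervals that support the stated PRO superiority objectives.

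**Working it through.** **The plan's own figure.** The only design calculation is for body weight: difference 6%, SD 8%, 25% dropout, 300 per arm (SAP section 5). Evaluable per arm: 300 × 0.75 = 225. SE = 8 × √(2/225) = 0.754, and 6/0.754 = 7.95, so power exceeds 0.9999 and the stated figure of more than 90% is met. It supplies nothing here except the 25%, which is a dropout assumption for body weight and not a PRO missing rate. I use it as an upper value with 10% beside it.

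**Which scores exist.** The Schedule of Activities, whose columns are misaligned in the extracted text, appears to place PROs at screening, Week 0, Week 36, Week 88 and ED. Protocol 4.1.1.2.2 confirms PROs at the ED visit and does not list them at Visit 99. SAP 1.3 times the ED visit at the point when the participant tells the site about stopping. Some ED scores may therefore fall more than 7 days after the last dose, outside the EAS. Week 88 scores collected off treatment fall outside it too.

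**How other endpoints are handled.** Under the same estimand, body weight, BMI, waist, laboratory and vital-sign changes use MMRM (Tables GPHN.4.2 and GPHN.4.3). Missing binary weight outcomes use MMRM predictions (SAP 4.4.1).

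**Attenuation.** Let D be the hypothetical Week 88 difference, d the share imputed in each arm (equal and unrelated to outcome), and u the average fraction of the 52-week divergence already present in the carried score.

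Share of D kept = 1 − d × (1 − u)

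| Score carried | u | d = 10% | d = 25% |
|---|---|---|---|
| ED, uniform dropout times, linear divergence | 0.50 | 0.95 | 0.875 |
| ED, earlier divergence | 0.75 | 0.975 | 0.94 |
| ED, later divergence | 0.25 | 0.925 | 0.81 |
| Week 36 for every missing participant | 0 | 0.90 | 0.75 |

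If half of the 25% have a usable ED score (u = 0.50) and half get Week 36, the share kept is 1 − 0.125 × 0.5 − 0.125 = 0.81.

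A simulated ANCOVA agrees. With an assumed true difference of 0.30 SD, 300 per arm and 25% missing at random, carrying Week 36 gave 0.224 (0.224/0.30 = 0.75). Using observed Week 88 scores only gave 0.299.

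**Interval width.** If carried scores have about the same residual variance as observed ones, LOCF reports the standard error of a trial with no missing scores. Relative to an analysis of observed scores, that is a factor of √(1 − d): 0.95 at 10% and 0.87 at 25%. In simulation with ED scores carried, 25% missing and a Week 36-to-88 correlation of 0.5, the standard errors were about 0.07 and 0.08. The nominal 95% interval covered the hypothetical difference about 91% of the time, through the shift and the narrowing together.

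**Direction.** With unequal shares and Week 36 carried, the expected difference is (1 − dT) × τ − (1 − dP) × π. Here τ and π are the mean Week 36-to-88 changes on tirzepatide and placebo, and dT and dP are the shares imputed in each arm. Take τ = −D, π = −2D, dT = 0.25 and dP = 0.10, all assumed. The result is −0.75D + 1.80D = 1.05D, an overestimate. Bias toward zero is therefore not guaranteed.

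**The case against.** The strongest reply is that SAP 4.1 already governs. It ties LOCF to an available ED measure, the EAS holds double-blind data only, and in the double-blind period Week 88 is the only scheduled PRO visit after randomization. On that reading Week 36 is never carried, and a participant with no ED score is simply not imputed.

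Much of this stands. A reader might infer that the plan will carry Week 36 forward and so lose a quarter of the PRO effect. The documents do not support that. The ED reading is at least as natural, and the 0.75 figure needs every one of the 25% to lack a usable ED score. For the Week 36-to-88 rows the question does not arise, because they satisfy the one-measure condition.

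The reply does not settle the Week 0-to-88 row, however. That row fails the one-measure condition, and its scope runs from Week 0. It also needs the Week 0 score, which the EAS definition read literally would exclude, so the EAS cannot decide which earlier scores are admissible.

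It is also fair that bias toward zero would be conservative for a superiority claim, that early PRO change after withdrawal would make the loss small, and that these endpoints carry no type I error control. None of this removes the estimand mismatch, which remains even when a valid ED score is carried.

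**Conclusion.** The mismatch holds. The SAP names a hypothetical target for the PRO scores and then uses a method that answers a different question, while handling its other continuous change endpoints under that estimand by MMRM. Carry-forward of Week 36 is an ambiguity between SAP 4.1 and Table GPHN.4.3 that must be reconciled. It is not a demonstrated plan.

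The size depends on assumptions outside the documents: the PRO missing rate, equal missingness unrelated to outcome, and the shape of divergence. Within those, the central illustration is a loss of about 5% of the difference at 10% missing and 12% at 25%. The worst case is 10% and 25%. A reader might conclude that LOCF always understates the effect here, but unequal or outcome-related missingness could push the estimate either way.

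The affected scores are additional secondary or exploratory. Primary and key secondary conclusions do not change. This is a cheap improvement.

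**What to change.** In Tables GPHN.4.3 and GPHN.4.4, replace LOCF as the main PRO method with one that is valid under missing at random and aligned with the hypothetical strategy. One suitable choice is multiple imputation within arm, using the Week 0 and Week 36 scores, on-treatment ED scores and on-treatment body weight as predictors, followed by the planned ANCOVA. ANCOVA on observed on-treatment Week 88 scores, adjusted for the Week 36 score, is a simpler alternative under a stronger assumption. With one scheduled PRO visit after randomization, MMRM would add little to it.

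State in SAP 4.1 and in the Week 0-to-88 row that scores from at or before randomization are never carried to Week 88. State also that an ED score counts only if it falls within the EAS window. Keep LOCF from post-randomization on-treatment ED scores as a sensitivity analysis.

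The cost is SAP wording, modest programming and somewhat wider intervals. The most an observed-scores analysis would add is a factor of 1/√(1 − d): about 5% at 10% missing and 15% at 25%. Imputation that uses informative ED scores should add less.

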4.5. Exploratory Endpoint(s) Analysis

Unless otherwise specified, exploratory efficacy analyses will be guided by the efficacy estimand using the same population as for primary analysis.

Table GPHN.4.4. Exploratory Efficacy Analysis

Objective	Relative to the efficacy measure:	Analysis Conducted
Compare tirzepatide MTD QW with placebo from Visit 2 (Week 0) to Week 88	Percentage of participants achieving 25% body weight reduction from Week 0 to Week 88	Refer to Section 4.4.1 for detail.
Compare tirzepatide MTD QW with placebo from randomization to Week 88	Percentage of participants whose BMI shifts between clinically relevant categories, i.e., from randomization to Week 88 (<25, 25 to <30, 30 to <35, 35 to <40, \geq 40)	Shift analysis will be conducted based on data from randomization to Week 88.
Compare tirzepatide MTD QW with placebo from randomization to Week 88	Percentage of participants whose lipid parameters shift between clinically relevant categories: 
 LDL-cholesterol (<70, 70 to <160, 160 to <190, \geq190mg/dL) HDL-cholesterol (male: <40, \geq40mg/dL, female: <50, \geq50mg/dL) Triglycerides (<150, 150 to <170, 170 to <500, \geq500mg/dL) 	Shift analysis will be conducted based on data from randomization to Week 88.
Compare tirzepatide MTD QW with placebo from randomization to Week 88	Percentage of participants achieving \geq 5% and \geq 10% body weight reduction from randomization to Week 88	Refer to Section 4.4.1 for detail.

Objective	Relative to the efficacy measure:	Analysis Conducted
Visualize tirzepatide MTD QW and placebo's percent weight loss change from Week 0 up to safety follow-up after 88 weeks	Percent body weight loss measured from Week 0 to 88 weeks plus 4 weeks safety follow-up	Time-course plot will be generated. Only the participants who complete the 88 weeks treatment period and have the safety follow-up (Visit 801) will be included.
Compare tirzepatide MTD QW with placebo from randomization to Week 88	
 • SF-36v2 acute form Bodily Pain domain (BP) • SF-36v2 acute form General Health domain (GH) • SF-36v2 acute form Vitality domain • SF-36v2 acute form Social Functioning domain (SF) • SF-36v2 acute form Physical-Component Summary score • SF-36v2 acute form Mental-Component Summary score • IWQOL-Lite-CT total score • IWQOL-Lite-CT Physical composite score • IWQOL-Lite-CT Psychosocial composite score • EQ-5D-5L utility score • EQ-5D-5L VAS score 	Data from randomization to Week 88 will be included. ANCOVA model with terms of treatment (tirzepatide MTD, placebo), all stratification factors, and corresponding score at randomization at Week 36 as a covariate. Missing data will be imputed using LOCF.

Abbreviations: ANCOVA = analysis of covariance; BMI = body mass index; HDL = high-density lipoprotein; IWQOL-Lite-CT = Impact of Weight on Quality of Life-Lite-Clinical Trials Version; LDL = low-density lipoprotein; MTD = maximum tolerated dose; QW = once weekly; SF-36 v2 acute form = Short Form-36 Version 2 Health Survey acute form; VAS = visual analog scale; VLDL = very low-density lipoprotein.

4.6. (Other) Safety Analyses

Unless specified otherwise, safety assessments for the double-blind treatment period will be based on the SS ([Table GPHN.3.1](#)). All data collected between randomization and the end date of study participation will be included, regardless of the adherence to study intervention.

Safety outcomes during the open-label lead-in treatment period will also be summarized for all enrolled participants. Detailed analyses can be found in [Appendix 3](#).

The statistical assessment of homogeneity of the distribution of categorical safety responses between tirzepatide MTD and placebo will be conducted using Fisher's exact test, unless specified otherwise.

The mean change from baseline differences among treatments at all scheduled visits will be assessed via an MMRM using REML. Unless specified otherwise, if the safety parameter is assessed at 88 weeks, then the model will include country/pooled country, sex, tirzepatide MTD dose at randomization, percent weight loss at randomization (<10% and $\geq 10\%$), treatment group, visit and treatment-by-visit interaction as fixed effects, and baseline value of the safety parameter as a covariate. To model the covariance structure within participants, the unstructured covariance matrix will be used. If this model fails to converge, the covariance structures specified in

Section 4.3.2.2 will be tested in order until convergence is met. If the data does not warrant the MMRM model, then ANCOVA model will be conducted.

For selected parameters, time-to-first-event analysis via the Cox-proportional hazards model may be conducted. Participants without the event will be censored at the end of study participation.

For participants experiencing the event, the “time-to-first-event” will be the time (in weeks) from first dose or randomization (depends on the event of interest and analysis feature, eg, for time to study discontinuation, time from first dose might be used; for time to AE during double-blind treatment period, time from randomization might be used) to first occurrence of the event.

Where necessary, the rate of events will be analyzed using a generalized linear mixed-effects model assuming the number of events follows a negative binomial distribution and with treatment as a fixed effect. The logarithm of days during the double-blind treatment period will be adjusted as an offset to account for possible unequal treatment duration of follow-up between participants.

4.6.1. Extent of Exposure

Summary of duration of follow-up (defined as time in days from date of randomization to the date of the last study visit) and/or duration on study treatment in double-blind treatment period (defined as time in days from date of randomization to date of last dose of study treatment plus 7 days) will be provided for all randomized participants by treatment group using data from randomization to 88 weeks plus safety follow-up (Visit 801).

For the summary of duration on study and study treatment in double-blind treatment period, the frequency and percentage of participants in the following ranges will be summarized by planned treatment group as well:

- >0 weeks
- ≥ 12 weeks
- ≥ 24 weeks
- ≥ 36 weeks
- ≥ 52 weeks.

In addition, the frequency and percentages of participants in the following study and study treatment exposure ranges may be summarized by planned treatment group:

- 0 week
- ≥ 0 to <12 weeks
- ≥ 12 to <24 weeks
- ≥ 24 to <36 weeks
- ≥ 36 to <52 weeks
- ≥ 52 weeks.

No p-values will be reported in these summaries as they are intended to describe the study populations rather than test hypotheses about them.

